## 8.7 Safety Analyses

This section describes the safety analyses that will be conducted till the end of the study period. i.e., the safety analyses on all data collected during the treatment period and all data collected in subjects who dropped-out during the study period.

All definitions relative to safety endpoints are detailed in the following sections.

Safety analyses will be conducted on the SAF population and will be performed for all safety variables specified below.

All safety data will be summarized by treatment group.

The safety analyses of changes from Baseline to a specific time point in safety variables (e.g., vital signs) will only include subjects from the SAF population who have data available for both the Baseline and the time point under consideration unless otherwise specified.

No statistical testing methods will be applied to statistically evaluate the differences on safety variables between treatment groups. Safety endpoint variables will be analyzed descriptively only.

### 8.7.1 Adverse Events

All AEs will be classified by SOC and PT according to MedDRA Version 22.0 or higher.

In summaries by SOC and PT, adverse events will be sorted by decreasing frequency within each SOC and PT. In summaries by PT, AEs will be sorted by decreasing frequency within each PT.

AE summary tables will be presented for TEAEs and AESIs separately by treatment and will include the number and percentage of subjects with any:

- TEAE/AESI
- TEAE/AESI related to study medication (AE will be defined as related if causality is definitely, probably or possibly or if causality assessment is missing)
- TEAE/AESI related to injection procedure (AE will be defined as related if causality is definitely, probably or possibly or if causality assessment is missing)
- Severe TEAE/AESI
- Severe TEAE/AESI related to study medication
- Severe TEAE/AESI related to injection procedure

- TEAE/AESI leading to discontinuation
- Study medication related TEAE/AESI leading to discontinuation
- Serious TEAE/AESI
- TEAE/AESI leading to death.

All TEAEs as well as all AESIs will be summarized by SOC, PT and treatment group using frequency counts and percentages (i.e., number and percentage of subjects with an event).

The number of events, as well as the number and rate of affected subjects will be reported by SOC and PT for all TEAEs and for all AESIs separately.

Adverse events will be separated to pre-treatment AEs and TEAEs. TEAEs are defined as all AEs with onset or worsening (increase in severity) after receiving first dose of study medication (independent of whether it is BoNT/A-DP or [REDACTED]). If it cannot be determined whether an AE is treatment-emergent due to a partial onset date, then it will be counted as such.

TEAEs will be summarized by system organ class (SOC) and preferred term (PT) (MedDRA). The number of events, as well as the number and rate of affected subjects will be reported.

TEAEs and AESIs (per SOC and PT) will also be summarized by seriousness, severity, relationship to study medication, and relationship to procedure using frequency counts and percentages (i.e., number and percentage of subjects with an event).

An individual by-subject listing will be provided for AE data.

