9. Photographs to be taken of subject's glabellar lines at maximum frown and at rest.
10. Treatment satisfaction will be determined using the FACE-Q Satisfaction with Outcome Scale. Results will be recorded in the eCRF.
11. Subjects will be monitored for AEs for 30 minutes after administration of the IMP. 30-minute post IMP administration, general, non-leading AE questioning as well as active AESI questioning must be performed.
12. General, non-leading AE questioning as well as active AESI questioning at each indicated visit. The first AESI questioning will be completed at Baseline Visit in order to obtain a full baseline status of any concomitant diseases PRIOR to the first IMP injection.

[figure not shown]
AESI Questioning: active questioning by guided review of systems per AESI manual. If an AESI is reported, a targeted physical examination around the area of the reported AESI must follow.

AE=adverse event; AESI=adverse event of special interest; D=distribution of subject diary; eCRF=electronic Case Report Form; GLS-I=Glabellar Line Scale-Investigator; GLS-S=Glabellar Line Scale-Subject; IMP=investigational medicinal product; obs=observation; R=return of subject diary

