## 14. ASSESSMENT OF SAFETY

### 14.1 Adverse Events

An AE is defined as any untoward medical occurrence in a subject administered an IMP that does not necessarily have a causal relationship with the treatment. An AE can therefore be any unfavorable and unintended sign (including an abnormal laboratory finding), symptom, or disease temporally associated with the use of an IMP, whether or not related to the IMP. AEs will be recorded from signing the ICF until the End of Study visit. SAEs and AESIs are subgroups of AEs as defined below. Any remark for AEs in general also applies to AESIs and SAEs.

Any pre-existing conditions or signs and/or symptoms present in a subject prior to the start of the study (i.e., before informed consent) should be recorded as Medical History; however, any increase in severity, frequency or duration of a pre-existing disease during the course of the study will be recorded as an AE. Clinically significant test results at Screening will be recorded as Medical History. Any untoward medical occurrence in a subject between ICF and administration of the study treatment will be recorded as a Pre-treatment Event on the Medical History page. Any untoward medical occurrence in a subject that occurs after treatment until the End of Study visit will be recorded as an AE. All AEs, AESIs, and SAEs must be recorded, irrespective of whether they are considered study drug related.

The investigator may contact the Sponsor's Medical Expert if additional information is needed for the assessment of AEs.

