### 14.2 Adverse Events of Special Interest

A specific concern in treatment with botulinum toxin products is the potential for local and distant spread of toxin effect, a unique set of safety concerns related to use of botulinum toxin drug products (draft guidance for industry *Upper Facial Lines: Developing Botulinum Toxin Drug Products*). Therefore, subjects will be instructed and educated on possible warning signs and precautions and on rare AESIs through the Subject Information Sheet (SIS). Safety data related to this specific potential effect should be obtained through directed query at each study visit and if an AESI (as listed below) is reported, a targeted physical examination should be conducted to evaluate for signs and symptoms of local and distant spread of toxin effect. AESI assessment and documentation is mandatory based upon the event term. An AESI must also be reported even if e.g., the duration of the event is considered unusual for an AESI or if the event is considered as being not related to the study drug. AESIs potentially suggestive of distant spread of toxin include:

accommodation disorder	dyspnea	Paresis
areflexia	extraocular muscle paresis	peripheral nerve palsy
aspiration	eyelid function disorder	peripheral paralysis
blurred vision	eyelid ptosis	pelvic floor muscle
botulism	facial palsy	weakness
bradycardia	facial paresis	pneumonia aspiration
bulbar palsy	fourth cranial nerve	pupillary reflex impaired
constipation	paresis	quadripareisis
cranial nerve palsies	hemiparesis	respiratory arrest
cranial nerve paresis	hypoglossal nerve paresis	respiratory depression
cranial nerve paralysis	hyporeflexia	respiratory failure
diaphragmatic paralysis	hypotonia	speech disorder
diplopia	monoparesis	third cranial nerve paresis
dry mouth	muscular weakness	trigeminal nerve paresis
dysarthria	paralysis	urinary retention
dysphagia	paralysis flaccid	vocal cord paralysis
dysphonia	paralytic ileus	vocal cord paresis
	paraparesis	

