#### **14.6.1 Reporting Serious Adverse Events and Adverse Events of Special Interest**

All SAEs and AESIs for all subjects occurring from the time of informed consent until the End of Study visit must be reported to Croma or their representative **within 24 hours** of the knowledge of the occurrence. If considered at least possibly related to study treatment, SAEs observed after the End of Study visit must also be reported.

Paper SAE/AESI forms should be completed at the site and emailed or faxed to the [REDACTED] **within 24 hours** of awareness of the event:

*The preferred way of submitting safety reports is via email; fax numbers are provided for backup.*

If a report is sent via email the completed and signed SAE/AESI or Pregnancy report form must be attached to the email; describing an event in the email text is not sufficient.

There may be situations when an SAE/AESI has occurred and the investigator has minimal information to include in the initial SAE/AESI report to Croma, or their representative. However, it is very important that the investigator always makes an assessment of causality for every event prior to transmission of the SAE/AESI report form. Minimum criteria are identifiable subject (number), suspect product (i.e., IMP or concomitant medication), an identifiable reporting source (investigator/study-site identification) and an event or outcome that can be identified as serious or as an AESI. The investigator may change his/her opinion of causality in the light of follow-up information, amending the SAE/AESI report form accordingly. The causality assessment is one of the criteria used when determining regulatory reporting requirements for SAEs.

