#### *Analysis of secondary safety endpoint 1 (AEs):*

Adverse events will be separated to pre-treatment AEs and TEAEs. TEAEs are defined as all AEs with onset or worsening (increase in severity) after receiving first dose of study medication (independent of whether it is BoNT/A-DP or █). If it cannot be determined whether an AE is treatment-emergent due to a partial onset date, then it will be counted as such.

Treatment-emergent AEs will be summarized by system organ class (SOC) and preferred term (PT) (MedDRA). The number of events, as well as the number and rate of affected subjects will be reported. Treatment-emergent AEs (SOC and PT) will also be summarized by seriousness, severity, relationship to study medication, and relationship to procedure. Treatment-emergent AESIs will be tabulated separately.

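### SAP 8.7.1 tabulates all AESIs where Protocol 15.4.2 specifies treatment-emergent AESIs, so an AESI arising between consent and dosing could be shown under a treatment group

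*SAP*

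**What the plan says.** **Analysis.** Protocol 15.4.2, on the adverse event endpoint, divides adverse events into pre-treatment events and TEAEs and then states: "Treatment-emergent AESIs will be tabulated separately". SAP 8.7.1 repeats the division but does not apply it to AESIs. Its overview is introduced by "AE summary tables will be presented for TEAEs and AESIs separately by treatment", and its system organ class and preferred term table by "All TEAEs as well as all AESIs will be summarized by SOC, PT and treatment group". The event counts and the tables by seriousness, severity and relationship likewise refer to AESIs without a treatment-emergent restriction. SAP section 9 declares three changes from the protocol, none about AESIs.

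**Endpoint.** Protocol 9.5.3 and SAP 4.3 name TEAEs, SAEs and AESIs over the whole study period. AESIs carry no treatment-emergent qualifier there.

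**Collection.** Protocol 4.1, footnote 12, places an active AESI query before the injection: "The first AESI questioning will be completed at Baseline Visit in order to obtain a full baseline status of any concomitant diseases". Protocol 14.2 adds: "AESI assessment and documentation is mandatory based upon the event term". Protocol 14.6.1 sets the reporting window: "All SAEs and AESIs for all subjects occurring from the time of informed consent until the End of Study visit must be reported". Protocol 14.1 has adverse events recorded from signature of the consent form, but also says that an untoward occurrence between consent and treatment "will be recorded as a Pre-treatment Event on the Medical History page".

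**The concern.** SAP 8.7.1 uses TEAEs and all AESIs side by side, having defined treatment emergence in the same section. A programmer would reasonably read them as two different sets and leave the treatment-emergent flag off the AESI tables. Any AESI in the adverse event data that began before the injection would then be shown under the product the subject later received.

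Protocol 7.6.2 and 14.2 single out local and distant spread of toxin effect as the specific safety concern for this class, and the AESI tables are where the two products are compared on it. An event that precedes dosing says nothing about either product. SAP 8.7.1 also treats a missing causality rating as related, so a pre-dose AESI without a rating would enter the rows for events related to study medication as well.

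**Working it through.** No figure in the documents bears on this point. The plan's one design calculation concerns the width of the interval for responder proportions. The check is a comparison of text, followed by a bound on size.

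**1. Are the two analysis instructions different?** Yes. Protocol 15.4.2 restricts to treatment-emergent AESIs and SAP 8.7.1 says all. The omission recurs in every AESI table in 8.7.1, and section 9 does not declare it.

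**2. Can a pre-dose AESI be in the adverse event data?**

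| Points towards yes | Points towards no |
|---|---|
| Protocol 14.1 and 14.6: adverse events recorded or monitored from consent | Protocol 14.1: events between consent and treatment go to Medical History |
| Protocol 14.2: AESI documentation depends on the event term | Protocol 14.1: conditions present before consent go to Medical History |
| Protocol 14.6.1: AESIs reportable from consent | Protocol 14.6.1 governs safety reporting forms, not the analysed data |
| SAP 7.2.2.1 and 8.7.1: rules for classing an adverse event as pre-treatment or TEAE | SAP 8.7: safety analyses described as covering the treatment period, which is not defined |

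The right-hand column keeps most pre-dose findings out if sites follow it. The left-hand column leaves a route open, because Protocol 14.1 and 14.6.1 can be read as conflicting instructions and the SAP provides for pre-treatment adverse events.

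**3. Which events could use the route?** Only an AESI with onset after consent and before dosing, entered as an adverse event. Protocol 4.1 limits Screening to 14 days and allows Screening, Baseline and treatment on one day, so the window runs from about zero to 14 days.

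**4. What does each event do?** With 100 subjects per arm, one affected subject adds 1/100 = 1.0 percentage point to that arm.

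**5. How many might there be?** The documents give no rate, so the following are assumptions. If AESIs arose in the background at 2% to 4% per 16 weeks (112 days), 14 days would give 2% × 14/112 = 0.25% to 4% × 14/112 = 0.5% per subject. With the number affected in each arm binomial (n = 100, probability q), the chance that the arms differ by two or more subjects from these events alone is the sum of P(A = a) × P(B = b) over |a − b| ≥ 2:

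| Assumed q | Expected subjects per arm (100q) | Chance arms differ by ≥ 2 subjects |
|---|---|---|
| 0.25% | 0.25 | 4% |
| 0.5% | 0.5 | 12% |
| 1% | 1 | 26% |

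All three rows assume that every such event is entered as an adverse event. Following the Medical History rule takes the counts towards zero.

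**The case against.** The strongest reply is that Protocol 14.1 already disposes of the matter. It sends conditions present before consent, and events between consent and dosing, to Medical History, and says that remarks about adverse events apply to AESIs too. SAP 8.4.3 then summarises medical history separately. The 14.6.1 duty is a 24-hour report on a paper form, and Protocol 14.6 distinguishes the safety database from the clinical one. This stands as far as it goes and makes the route narrow. It does not close it, because the SAP itself expects pre-treatment events among the adverse events and gives rules for classing them.

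It can also be said that the SAP follows the protocol's endpoint wording in 9.5.3, so the inconsistency starts inside the protocol. That is right. The conflict is with the analysis instruction in 15.4.2.

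Three stronger readings are tempting and are not supported:

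- **Common complaints on the AESI list (constipation, dry mouth, blurred vision) found at the pre-dose query will fill the tables.** Those that predate consent are Medical History under Protocol 14.1 and fall outside the 14.6.1 window.
- **The comparison will be diluted substantially.** No risk ratio is planned. Adding equal percentages to both arms leaves the difference unchanged. Pre-dose rates of several percent would be hard to credit in a window of at most 14 days.
- **One product is disadvantaged.** Events before dosing can fall in either arm, so any imbalance is by chance and has no expected direction.

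**Conclusion.** The mismatch between SAP 8.7.1 and Protocol 15.4.2 is real, runs through all the AESI tables and is undeclared. Its practical effect is possible but probably small: it requires an AESI with onset in the 0 to 14 days between consent and dosing, entered as an adverse event despite the Medical History instruction. Each such subject moves an arm's AESI percentage by 1 point. Under the assumed 0.25% to 1% per subject, that is 0.25 to 1 subject per arm before allowing for correct routing. No hypothesis test is affected, since all safety analyses are descriptive. The correction is still worth making because AESI counts may be low, spread of toxin effect is the named safety concern, and the flag that resolves it already exists.

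**What to change.** 1. In SAP 8.7.1, restrict every AESI table (overview, system organ class and preferred term, event counts, severity, seriousness, relationship) to treatment-emergent AESIs, using the SAP's existing rule of onset or worsening after the first dose. Applying the whole rule matters: sorting on onset date alone would remove a pre-dose AESI that worsens after the injection, and that event belongs in the tables.
2. List separately only those AESIs that are not treatment-emergent.
3. Reconcile Protocol 14.1 with 14.6.1, in the protocol or the completion guidelines, so that sites know where an AESI arising between consent and dosing is recorded.
4. If the sponsor does intend to tabulate all AESIs, declare it in SAP section 9 as a change from Protocol 15.4.2 and label the tables accordingly.

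The cost is SAP wording and one filter on a flag that is already derived. If sites have followed the Medical History rule throughout, no number changes.

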### 8.7.2 Vital Signs

The analyses of variables for vital signs (VS) will focus on the evaluation of the change from Baseline to the scheduled time points after Baseline. Descriptive statistics by visit and of changes from Baseline to each post-Baseline visit by treatment will be presented.

An individual by-subject listing will be provided for VS data.

### 8.7.3 Physical Examinations

At Screening and the End of Study visit, a full physical examination will be performed by the investigator. A full physical exam will include neurological assessment (including extraocular movements and cranial nerves) as well as assessment for muscle weakness. In addition, if the subject reports an AESI (as detailed in the AESI Manual) a focused physical examination by the physician will also be undertaken to evaluate these symptoms. Any clinically relevant abnormal finding will be documented in the eCRF as AE/medical history.

## Statistical Analysis Plan (SAP)

**CROMA**  
est. 1976

All physical examination data and abnormalities will be listed only.

### 8.8 Other Analysis

#### 8.8.1 Subgroup Analysis

The following subgroup analyses will be performed for the co-primary efficacy endpoints:

- a) Subgroup analysis by site
- b) Subgroup analysis by Country
- c) Subgroup analysis by Geographic Region (Europe and US/Canada)
- d) Previous use of Botulinum
- e) Subgroup analysis by race (American Indian or Alaskan Native, Asian, Black or African American, Native Hawaiian or Other Pacific Islander, Caucasian (Including Hispanic or Latino and Other))
- f) Subgroup analysis of:
  - subjects with previous use of botulinum toxin by site
  - naïve subjects by site
- g) Subgroup analysis by Fitzpatrick skin type (TYPE I, TYPE II, TYPE III, TYPE IV, TYPE V, and TYPE VI)
- h) Subgroup analysis by sex
- i) Subgroup analysis by ethnicity (Hispanic or Latino versus Not Hispanic or Not Latino)
- j) Subgroup analysis by age groups (below 65 years, 65-74 years and  $\geq$  75 years)
- k) Subgroup analysis by additional age groups (below 65 years versus 65 years and older).

Subgroup analyses will be performed on the FAS population. Two-sided 95% CIs using the Newcombe method will be calculated for the difference between BoNT/A-DP and [REDACTED]. Two-sided 95% CIs for the responder rates in the BoNT/A-DP and the [REDACTED] treatment groups will be calculated using Wilson scores, when relevant.

### 8.9 Interim Analysis

No interim analyses are planned.

### 9 CHANGES TO PLANNED ANALYSIS FROM STUDY PROTOCOL

- Section 13.1.1 of the protocol incorrectly references the primary efficacy endpoint as the composite endpoint of the investigators' and the subjects' assessments of line severity at maximum frown after treatment with BoNT/A-DP compared to [REDACTED] at Week 4. No analyses are planned on the composite endpoint.
- Subgroup analyses by country and geographic region will also be performed.
- The Newcombe method, rather than the Clopper-Pearson method as referenced in the protocol, will be used to derive CIs when comparing the two treatment groups.

# Statistical Analysis Plan (SAP)

## 11 APPENDICES

### Appendix A - Visit Window

Analyses will be performed by nominal visit, irrespective of any time window deviations. For the End of Study (EOS) visit, the following criteria will be applied:

- The nominal visit will be used throughout for all subjects who have not discontinued.
- For discontinued subjects, the EOS data will be assumed to be the preceding visit where no assessments are available.
- For discontinued subjects, the EOS data will be assumed to be the visit following the preceding visit if for the preceding visit an assessment is already available.
- Unless duplicate records are present in the database, there should be no duplicate data per visit.

The following examples illustrate the approach:

## Statistical Analysis Plan (SAP)

**CROMA**  
est. 1976

### **Numbering of Visits**

Visit numbers correspond with specific treatment and assessments as outlined in the protocol Schedule of Events, [Table 2](#).
